Anti-olipudase alfa antibody (IgG)	Quarterly	During the study period, for the switch from Process B to Process C (■) or from Process C (■) to Process C (■), collection will be monthly for the first 6 months after starting the new process, and quarterly after that.							
Neutralizing antibodies		In patients who develop anti-olipudase alfa antibody (IgG)							
IL-6, IL-8, and calcitonin		In case of suspected cytokine release syndrome							
Immune response assessment in case of IAR suggestive of hypersensitivity reaction									
Anti-olipudase alfa antibody (IgG)		At least 3 days after or prior to the next infusion in case of a moderate/severe or recurrent IAR suggestive of a hypersensitivity reaction							
Neutralizing antibodies		In patients who develop anti-olipudase alfa antibody (IgG)							
Anti-olipudase alfa antibody (IgE)		At least 3 days after or prior to the next infusion in case of a moderate/severe or recurrent IAR suggestive of a hypersensitivity reaction							
Serum tryptase and complement activation		Within 1 to 3 hours of a moderate/severe or recurrent IAR suggestive of a hypersensitivity reaction							
Skin testing	If necessary								

^a Patients will receive olipudase alfa every 2 weeks (± 3 days). Quarterly visits will occur at the site. If the site visit is not possible during a regional or national emergency declared by a governmental agency such as the COVID-19 pandemic due to site closure or extenuating circumstances that prevent an in-person site visit and home infusion is already approved for the eligible patient, quarterly visits will be done at home. Quarterly visit specific assessments that need a site visit will not be done at that time and will be done as unscheduled as soon as site visits become available. In such a case, some of the quarterly visit assessments may be done by home nurse (eg, lab sampling) and by the site through the phone (eg, Health-related quality of life instruments). Telehealth visits are an acceptable alternative to site visits if the site visit is not possible during a regional or national emergency declared by a governmental agency such as the COVID-19 pandemic due to site closure or extenuating circumstances that prevent an in-person site visit, in accordance with institutional policy and with applicable country-specific regulations.

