Note: The visit schedule is calculated in reference to the first infusion of the patient's previous study. The ± 14 day window applies only to assessments not linked to the time of the infusion. For infusions and assessments closely linked to the time of the infusion (eg, abbreviated physical exams, vital signs), the Q2W visit window of ± 3 days remains.							
Visit/timing	Every 2 weeks (± 3 days)	W14 ^a QV (± 14 days)	W26 ^a QV (± 14 days)	W38 ^a QV (± 14 days)	W52 ^a QV (± 14 days)	Study completion, patient discontinuation, or withdrawal ^b	Safety follow-up phone call ^c
Pediatric health outcome questionnaires (PedsQL, PedsQL Multidimensional Fatigue Scale, PedsQL Pediatric Pain Questionnaire)		X		X		X	
Pharmacokinetics ^{f, l}					X		
Immune response assessments							
Anti-olipudase alfa antibody (IgG)	Quarterly	During the study period, for the switch from Process B to Process C (█) or from Process C (█) to Process C (█), collection will be monthly for the first 6 months after introducing the new process, and quarterly after that.					
Neutralizing antibodies	In patients who develop anti-olipudase alfa antibody (IgG)						
IL-6, IL-8, and calcitonin	In case of suspected cytokine release syndrome						
Immune response assessment in case of IAR suggestive of hypersensitivity reaction							
Anti-olipudase alfa antibody (IgG)	At least 3 days after or prior to the next infusion in case of a moderate/severe or recurrent IAR suggestive of a hypersensitivity reaction						
Neutralizing antibodies	In patients who develop anti-olipudase alfa antibody (IgG)						
Anti-olipudase alfa antibody (IgE)	At least 3 days after or prior to the next infusion in case of a moderate/severe or recurrent IAR suggestive of a hypersensitivity reaction						
Serum tryptase and complement activation	Within 1 to 3 hours of a moderate/severe or recurrent IAR suggestive of a hypersensitivity reaction						
Skin testing	If necessary						

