9.5 SAMPLED BLOOD VOLUME

For all pediatric patients, no more than 7 mL/kg of blood will be collected during any 8-week period. Additional blood samples may be collected at the investigator's discretion for patient safety monitoring.

If a PK or IgG sample collection for the planned introduction of drug product from Process C(█) was erroneously taken, the future sample collection will be adjusted according to the blood volume allowed per each age cohort in order to avoid excessive blood withdrawal. For specific details, please refer to Study Manual.

[Table 17](#) shows the approximate sampled blood volume in patients ages 12 to <18 years old in the first 5 years.

Table 17 - Approximate sampled blood volume in patients ages 12 to <18 years in the first 5 years

Assessment	Volume (mL) per sample	Number of samples per year	Total (mL) per year
Liver function, clinical chemistry, and lipid profile	5.0	4	20.0
Hematology	2.0	4	8.0
Coagulation	3.6	4	14.4
Safety biomarkers	6.5	4	26.0
Efficacy biomarkers	10.0	4	40.0
Serum bone-specific AP and C-telopeptide	2.5	4	10.0
Metabolites in plasma and/or DBS	3.2	4	12.8
Anti-olipudase alfa IgG and neutralizing antibodies in IgG-positive patients	3.5	4	14.0
Olipudase alfa pharmacokinetics	1.5	7	10.5
		Approximate total per year	155.7
		Approximate total per 5 years	778.5

AP=alkaline phosphatase

Table 18, Table 19 show the additional approximate sampled blood volume in patients ages 12 to <18 years old with an olipudase alfa manufacturing scale change or manufacturing process update respectively. Not all of the patients will be exposed to both changes; therefore, blood volume would be calculated individually. To avoid excessive blood volume withdrawn, if similar assessment is regularly scheduled (IgG, PK or hematology and coagulation) in the same month, priority is given to manufacturing scale or updated manufacturing process update assessments and the regular similar assessments may be canceled.

Table 18 - Additional approximate sampled blood volume in patients ages 12 to <18 years with an olipudase alfa manufacturing scale change

Assessment	Volume (mL) per sample	Number of samples	Total (mL)
Anti-olipudase alfa IgG and neutralizing antibodies in IgG-positive patients	3.5	1 sample per month for 6 months	21.0
Olipudase alfa pharmacokinetics - prior to manufacturing scale change	1.5	7	10.5
Olipudase alfa pharmacokinetics - post manufacturing scale change	1.5	7	10.5
Approximate additional volume per study			42.0

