#### **2.1.3.3 Laboratory safety parameters**

Clinical laboratory data consists of blood analysis, including hematology, clinical chemistry, and urinalysis. Clinical laboratory values will be converted into standard international units, and both US conventional units and international units will be used in all displays for continuous variables.

The following clinical laboratory test results are assessed as part of safety profile:

- Clinical chemistry: Sodium, potassium, calcium, chloride, blood urea nitrogen, creatinine, lactate dehydrogenase, total protein, albumin, glucose, phosphorus, and creatine kinase. These are scheduled for every 3 months.
- Liver function tests: ALT, AST, AP, gamma-glutamyl-transferase, total bilirubin, and direct bilirubin. These are scheduled for every 3 months.
- Hematology: Complete blood count with differential and platelet count, including hematocrit, hemoglobin, red blood cell, white blood cell, platelet, neutrophil, lymphocyte, monocyte, eosinophil, and basophil counts. These are scheduled for every 3 months.
- Coagulation studies: Prothrombin time (Protome), partial thromboplastin time, international normalized ratio, and D-dimer. These are scheduled for every 3 months.
- Urinalysis: Dipstick for glucose, protein, hemoglobin, leukocytes, ketones, and bilirubin. These are scheduled for every 3 month visit in this study.
- Safety biomarkers: hsCRP, iron, ferritin, cardiac troponin I, IL-6, IL-8, ceramide in plasma and calcitonin. These are scheduled for every 3 month visit in this study.
- Immune response assessments: anti-olipudase alfa IgG antibodies. These are scheduled for every 3 month visit in this study.

- If an IAR is anticipated to be a hypersensitivity reaction, additional laboratory parameters will be evaluated as soon as possible: tryptase activity and complementation activation, IgG and IgE. A skin testing may also be performed.
- If an IAR is anticipated to be a cytokine release syndrome (CRS), additional laboratory parameters will be evaluated as soon as possible: IL-6, IL-8, calcitonin.

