#### **2.4.7.11 *Immune response assessments***

Data listings will be provided to display results of anti-olipudase IgG antibody, neutralizing antibody, anti-olipudase alfa IgE antibody, serum tryptase activity, complement activation, and skin testing performed. If IgG antibody titer value is reported as <xx, the numeric value will be imputed as xx, the minimum required dilution (MRD), and used for summary purposes. Listing will provide results as reported as well as results as imputed.

A patient with at least one anti-drug antibody (ADA) response available in the database is considered evaluable.

A patient whose ADA status is positive at baseline is considered to have pre-existing ADA.

A patient whose ADA status is positive anytime post-baseline and is negative or missing at baseline is considered to have treatment-induced ADA.

A patient whose ADA status is positive at baseline (pre-existing ADA) and the ADA titer level anytime post-baseline is significantly higher than that at baseline is considered to have treatment-boosted ADA. A difference in titer values between 2 samples representing greater than or equal to twice the dilution level is considered significant. In other words, the post-baseline titer value divided by the baseline titer value will be greater than or equal to 4 to be considered significant. For example, if baseline titer value is 50, the post-baseline titer value has to be  $\geq 200$ .

For patients with treatment-induced ADA, the following 3 ADA responses are defined.

**Transient ADA response** is defined as:

- Treatment-induced ADA detected only at one sampling time point post-baseline (excluding the last sampling time point).
- Treatment-induced ADA detected at two or more sampling time points post-baseline, where the first and the last ADA-positive samples (irrespective of any negative samples in between) are separated by a period of less than 16 weeks, and the subject's last sampling time point is ADA-negative.

**Persistent ADA response** is defined as:

- Treatment-induced ADA detected at two or more sampling time points post-baseline, where the first and the last ADA-positive on-treatment sample (irrespective of any negative samples in between) are separated by at least 16 weeks.
- Treatment-induced ADA detected in the last two sampling time points, irrespective of the time period in between.

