The assessment of ADA incidence and characterization by manufacturing process B compared with Process C will be conducted through pooled analyses and presented in the integrated summary of immunogenicity. The assessment of immunogenicity and safety by Processes will be presented in the integrated summary of safety (ISS).

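### IgG sampling rises to monthly for six months after a process switch and the SAP's ADA definitions do not align samples, so a Process B versus C comparison built on them would have unequal ascertainment in patients who switch

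*Protocol*

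**What the plan says.** **Sampling.** Protocol 1.1 (Table 1) states for IgG after a switch that "collection will be monthly for the first 6 months after starting the new process, and quarterly after that". The pediatric charts, for example Table 5, say that "collection will be monthly for the first 6 months after introducing the new process, and quarterly after that". The post-switch rule is essentially the same through Table 8. Beyond Year 5 the contrast is sharper: Tables 3, 4, 9 and 10 list no routine quarterly IgG before a switch, and Tables 9 and 10 list none after the monthly phase.

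Protocol 9.5 gives the counts for ages 12 to under 18. Table 17, row "Anti-olipudase alfa IgG and neutralizing antibodies in IgG-positive patients", has 4 samples a year. Table 18 has "1 sample per month for 6 months" after a scale change. Where the two fall in the same month, "priority is given to manufacturing scale or updated manufacturing process update assessments and the regular similar assessments may be canceled".

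**Analysis.** SAP 2.1.3.3 describes "anti-olipudase alfa IgG antibodies. These are scheduled for every 3 month visit in this study" and does not mention the monthly samples. SAP 2.4.7.11 then defines:

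- treatment-induced ADA: any positive sample after baseline in a patient not positive at baseline;
- transient ADA: a single positive time point other than the last, or positives spanning under 16 weeks with a negative last sample;
- persistent ADA: first and last positive samples ("irrespective of any negative samples in between) are separated by at least 16 weeks"), or positives at the last two time points whatever the gap;
- peak titer: the highest titer per patient.

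No rule thins, weights or aligns samples. SAP 2.6.3 applies no visit windows, and SAP 2.6.4 keeps unscheduled values for any-time summaries. On process, SAP 2.4.7.11 says: "The assessment of ADA incidence and characterization by manufacturing process B compared with Process C will be conducted through pooled analyses", with the results going to the integrated summary of immunogenicity.

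**The concern.** Each of these definitions responds to how often a patient is sampled. More samples give more chances of a positive result and of catching the highest titer. They also allow first and last positives to meet a 16-week span that adjacent quarterly visits cannot reach. A patient who switches is sampled more densely just after starting the new process than on the old one. Some of any difference in ADA between processes could then come from the schedule.

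Immune response is among the primary safety endpoints (protocol 9.1.1). Treatment-emergent ADA status also defines the spleen and platelet subgroups in SAP 2.4.8.15 and is explored against PK in SAP 2.4.9.2. Version lag does not explain the SAP's three-monthly wording. The SAP is based on Amendment 04, and the protocol's own history (17.2.6, item 13) dates monthly sampling after a scale change to Amendment 01.

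**Working it through.** **1. The plan's own counts.** Table 17: 3.5 mL x 4 = 14.0 mL a year, so 2 samples per six months. Table 18: 3.5 mL x 6 = 21.0 mL; table total 21.0 + 10.5 + 10.5 = 42.0 mL. Both reproduce. In the six months after a switch this gives about 6 samples against 2; in the first twelve months, 6 + 2 = 8 against 4. "About" is needed because section 9.5 permits, but does not require, cancelling the coinciding routine sample.

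**2. Model.** The documents give no episode lengths or positivity rates, so these are assumptions. Take one unbroken positive episode of D weeks, with onset uniform over a stated period after the switch (week 0) and all later samples negative.

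- Post-switch schedule: every 26/6 = 4.33 weeks (4.33, 8.67, 13, 17.33, 21.67, 26), then 39, 52 and so on.
- Quarterly schedule: 13, 26, 39 and so on.

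**3. Detection**, onset in weeks 0-13 or 0-26. The probability is D divided by the sampling interval, capped at 1.

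| D (weeks) | Post-switch | Quarterly |
|---|---|---|
| 4 | 4/4.33 = 92% | 4/13 = 31% |
| 8 | 100% | 8/13 = 62% |
| 12 | 100% | 12/13 = 92% |
| 13 or more | 100% | 100% |

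**4. Persistent class (span of at least 16 weeks).** Two adjacent quarterly positives span 13 weeks (12 or 14 on the pediatric visit weeks), so three are needed: 26 weeks, or 24-28 on the pediatric grid. Monthly sampling needs four intervals, 4 x 4.33 = 17.33 weeks.

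For D = 20 on the post-switch schedule, onset must fall in one of these windows, each 2.67 weeks wide:

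- 1.67-4.33 (positives from 4.33 to 21.67);
- 6.00-8.67 (positives from 8.67 to 26);
- 19.00-21.67 (positives from 21.67 to 39).

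Onset in weeks 0-13: 2 x 2.67/13 = 41%. Onset in weeks 0-26: 3 x 2.67/26 = 31%. On the quarterly schedule a 20-week episode holds at most two samples, so 0%.

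Simulation of the same model, onset in weeks 0-13:

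| D (weeks) | Post-switch | Quarterly |
|---|---|---|
| 16 | 0% | 0% |
| 18 | 10% | 0% |
| 20 | 41% | 0% |
| 24 | 67% | 0% |
| 30 | 97% | 31% |
| 34 | 100% | 61% |
| 39 | 100% | 100% |

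On the actual pediatric visit weeks, the quarterly results are 8% at 26 weeks and 39% at 30.

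**5. Dilution over time.** With onset anywhere in the first 104 weeks after a switch, detection of a 4-week episode is 12 x 4/104 = 46% against 8 x 4/104 = 31%. A 20-week episode is classed persistent in 3 x 2.67/104 = 8% against 0%.

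**6. A cruder check.** If samples were independent with positive rate p, the chance of any positive in six months is 1-(1-p)^6 against 1-(1-p)^2. This gives 5.9% against 2.0% at p = 1%, and 26.5% against 9.8% at p = 5%. Independence is unrealistic for antibody episodes, so this is only indicative.

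**7. The last-two-samples rule.** This route to persistence was not modelled. SAP 2.4.7.11 takes the final assessment at the data cutoff. A cutoff inside the monthly phase would let two positives a month apart count as persistent, where quarterly sampling would need them about three months apart.

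**The case against.** The best defence is that this SAP contains no by-process ADA table. All its listed ADA outputs are per patient over the whole treatment epoch, and its by-process work in 2.4.8.15 covers spleen volume and platelets. The Process B versus C comparison of ADA goes to a pooled summary whose sample handling is not shown and might already deal with this. That stands: for that comparison the documents show a risk, not a defect. That every sample counts is likewise an inference from the absence of any restriction, though it is the natural reading.

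A reader might infer that the plan makes the newer process look more immunogenic. The documents do not support a fixed direction:

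- The observation period includes the original studies, whose ADA sampling frequency is not given, so Process B time may also contain dense sampling.
- Some pediatric patients started on Process C and have no B-to-C monthly phase.
- A patient already positive before a switch counts as positive whatever follows.

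It is also fair that the safety analysis is descriptive (protocol 11.6.3), in about 25 patients, with antibody results listed as reported.

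Finally, replacing the all-sample classes with a quarterly grid would have a price. The amendment history records the monthly samples as a regulator's request, and a quarterly grid turns the 16-week cut into 24-28 weeks for everyone. That argues for keeping the all-sample tables and adding the grid version beside them.

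**Conclusion.** The point holds in a limited form. The sampling change is real, the SAP does not describe it, and its ADA definitions depend on it. For patients who switch, a by-process comparison built on those definitions would have unequal ascertainment.

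The size rests on assumed episode lengths and on onset in the first 13 to 26 weeks after a switch: 92% against 31% for detecting a 4-week episode, and 31-41% against 0% for classing a 20-week episode as persistent. It shrinks for later onset. There is no effect on detection from about 13 weeks, or under the 16-week span rule on class below about 17 or above about 39 weeks. No effect on peak titer was calculated. The net direction across the pooled data cannot be determined from these documents, and they do not show that any planned result is biased towards either process.

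**What to change.** 1. In SAP 2.1.3.3, state that IgG is sampled monthly for six months after a process switch.
2. Keep ADA incidence and the transient/persistent classes on all samples as the study's main ADA tables.
3. In SAP 2.4.7.11, state that any by-process ADA comparison, including the pooled one, is also made on a common quarterly grid. After a switch, use the samples nearest month 3 and month 6, then the quarterly samples. Show this beside the all-sample result.
4. State that a process difference is not attributed to the product unless it also appears on the matched grid.

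The cost is SAP wording, one sample-selection flag and one extra table; no new data are needed. The matched version uses fewer samples, so it is less precise and less sensitive to short episodes. Nearest-sample selection is needed because visits are anchored to the first infusion of the previous study, not to the switch date.

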1.6 STUDY FLOW CHART: PHARMACOKINETIC SAMPLING

For both adult and pediatric patients, PK testing will only occur yearly (up to 5 years) and upon the introduction of a drug product from Process C(█) or Process C(█) at any time during the study. For Process C(█), if treatment is not interrupted, PK collection will take place at the patient's last infusion under the current manufacturing scale and at the first infusion Process C(█). For introduction of drug product from Process C(█), if treatment is not interrupted, PK sample collection will take place at the second infusion under the Process C(█). In case reintroduction of olipudase alfa coincides with introduction of drug product from Process C(█) or Process C(█), PK samples will be collected at the infusion at which patients receive their usual dose of olipudase alfa under the new process. For introduction of drug product from Process C(█), if treatment is not interrupted, PK sample collection will take place at the second infusion under Process C(█).

If a PK sample collection for the planned introduction of drug product from an updated manufacturing process was erroneously taken, the future sample collection will be adjusted according to the blood volume allowed per each age cohort in order to avoid excessive blood withdrawal. For specific details, please refer to Study Manual.

Table 11 - Pharmacokinetic sampling in adults

Week	Before infusion ^a	End of infusion	Hours after infusion ^b					
			1	4	8	24	48	96
12-month visit (up to 5 years)	X	X	X	X	X	X	X	X
If a manufacturing scale change or an updated manufacturing process occurs	X	X	X	X	X	X	X	X

a Pre-infusion sample to be collected within 24 hours before infusion start.

b Sample collections are to be within ± 10 minutes for those <8 hours from infusion end and ± 3 hours for those ≥ 8 hours after infusion end.

Table 12 - Pharmacokinetic sampling in pediatric patients

Visit	Age	Time from end of infusion ^a						
		Pre-infusion ^b	End of infusion	2 h	6 h	24 h	48 h	96 h
12-month visit or if introduction of a drug product from a manufacturing scale change or an updated manufacturing process occurs	Adolescent	X	X	X	X	X	X	X
	Child	X		X	X	X	X	X
	Infant/early child	X		X		X	X	X

a Sample collections are to be within ± 10 minutes for those <8 hours from infusion end and ± 3 hours for those ≥ 8 hours after infusion end.

b Pre-infusion sample to be collected within 24 hours before infusion start.

3 LIST OF ABBREVIATIONS

ABAS:	Adaptive Behavior Assessment System
ACE:	angiotensin converting enzyme
AE:	adverse event
AP:	alkaline phosphatase
Apo:	apolipoprotein
APR:	acute phase reaction
ASM:	acid sphingomyelinase
ASMD:	acid sphingomyelinase deficiency
ASMKO:	acid sphingomyelinase knock out
AUC _{0-∞} :	area under the concentration-time curve from time 0 to infinity
AUC _{last} :	area under the concentration-time curve
BFI:	Brief Fatigue Inventory
BMD:	bone mineral density
BMI:	body mass index
BPI:	Brief Pain Inventory
CCL-18:	chemokine (CC-motif) ligand 18
C _{eo} i:	concentration at the end of infusion
CL:	apparent total body clearance
C _{max} :	maximum concentration observed
CO ₂ :	carbon dioxide
CRF:	case report form
CRS:	cytokine release syndrome
CS:	clinically significant
DBS:	dried blood spot
DL _{CO} :	diffusing capacity of the lung for carbon monoxide
DMC:	Data Monitoring Committee
DNA:	deoxyribonucleic acid
DP-3:	Development Profile-Third Edition
DXA:	dual-energy X-ray absorptiometry
ECHO:	echocardiogram
EOT:	end of treatment
FEV ₁ :	forced expiratory volume in the first 1 second
FVC:	forced vital capacity
HDL:	high-density lipoprotein
HRCT:	high resolution computed tomography
IAR:	infusion associated reaction
ICH:	International Council on Harmonisation
IEC:	independent ethics committee
IL:	interleukin
ILD:	interstitial lung disease
IMP:	investigational medicinal product

IRB:	institutional review board
IV:	intravenous
LDL:	low-density lipoprotein
LFT:	liver function test
MIP:	macrophage inflammatory protein
MRI:	magnetic resonance imaging
NCS:	not clinically significant
NE:	not evaluable
NPB-HAQ:	Niemann-Pick B Health Assessment Questionnaire version 2
NPD:	Niemann-Pick disease
O ₂ :	oxygen
PCSA:	potentially clinically significant abnormality
PD:	pharmacodynamic
PedsQL:	Pediatric Quality of Life
PFT:	pulmonary function test
PIP:	pediatric investigational plan
PK:	pharmacokinetic
PT:	preferred term
SAE:	serious adverse event
SF:	Short Form
SF-36:	Short Form-36
SFCRQ SAS:	Chronic Respiratory Disease Questionnaire Self-administered Standardized
SOC:	system organ class
t _{1/2z} :	terminal half-life associated with the terminal slope (λ_z)
t _{max} :	time to reach maximum concentration
VLDL:	very low-density lipoprotein
V _{ss} :	apparent volume of distribution at steady-state
β -HCG:	beta-human chorionic gonadotropin

